Lowering and maintaining sUA concentrations below the level of 'supersaturation' is absolutely essential in reducing the total body urate burden and achieving long-term benefits. Targeting a slightly lower threshold of < 6.0 mg/dl accounts for both the issues of day-to-day variability in sUA and assay imprecision (estimated in College of American Pathologists Proficiency Testing [CAP PT] to approach 4 to 5%). Although the predominance of literature suggests no significant diurnal variation in sUA (73, 74), others have suggested a small degree of such variability approaching 0.5 mg/dl (75). In particular, this level of sUA is considered an evidence-based target for treatment, and necessary to achieve outcomes pertinent to patients, such as reduction of flare frequency (7, 76). Understanding its essential role in gout treatment, we have adopted the biochemical threshold of a sUA concentration below 6.0 mg/dL as a secondary end-point, and one which regulatory agencies require for approval (11, 13).

To facilitate point-of-care ULT dose titration, all sUA measurements will be performed by the clinical laboratory at the participating study site. Importantly, sUA measurement is internationally standardized and readily accessible across all participating clinical laboratories. The prevailing technique used for sUA measurement used in the U.S. (including VA centers and RAIN sites) uses the Trinder reaction with uricase, an assay that has been shown to be highly reliable with between-laboratory and between-method coefficients of variation routinely below 5% (77).

- 3) Determining if gout flares in Phase 3 differ in those who reach a target sUA of < 6.0 mg/dl compared with those who do not by 48 weeks.

As detailed above, achieving a sUA goal of <6.0 mg/dl is a universally recommended treatment goal for ULT in practice as well as regulatory trials. However, the true relationship of achieving this target with reducing gout flares has not been well documented in long-term clinical trials. The design of this trial will allow us to address this important question. Specifically, we will compare the gout flare rates in Phase 3 of those who did and did not achieve a sUA of < 6.0 mg/dl at the end of Phase 2.

- 4) The impact of study treatments and sUA levels on health-related quality of life.

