A strategy of dose titration for each treatment will be employed to bring as many participants as possible below the threshold of sUA < 6.0 mg/dl, established by guidelines and recommendations (7). The Phase 1 titration is intended to bring sUA < 6.0 mg/dl within 24 weeks. All participants will be analyzed during Phase 3 regardless of whether their sUA is < 6.0 or \geq 6.0 mg/dl. We expect that roughly equal numbers of participants in each study arm will reach this threshold. We expect that 75% - 80% participants will have a mean sUA < 6.0 mg/dl across the last 3 study visits occurring during Phase 2 at 36, 42, and 48 weeks. For secondary analysis, we define the binary outcome, mean sUA < 6.0 mg/dl as a treatment success and mean sUA \geq 6.0 mg/dl, as a treatment failure.

Choice of a Bound, B, for the Non-inferiority Test

Non-inferiority tests require expert choice of a bound, B, larger than the true difference, D, between the treatment proportions of participants with flare events (the proportion for febuxostat minus the proportion for allopurinol). The bound marks where clinicians might begin to doubt that the difference, D, is very small and close to zero. Seven rheumatologists on our Planning Committee, selected for their expertise in gouty arthritis and clinical trial design, chose B = 8%.

The null hypothesis will be rejected if U, the upper limit on the one-sided 95% confidence interval on the difference between the two flare-event rates (D), is less than B = 8%. (See Figure 1) If U exceeds B then this indicates that the true difference may be large and that allopurinol is inferior to febuxostat. (See Figure 2)

It is important to note that our choice of a bound is more conservative when compared to many other recent studies. Previous studies have chosen the true bound to be 10% and a true difference in the proportions to be 0% (11). For the non-inferiority test, this more conservative estimate requires CSP 594 to enroll a larger sample size.

Primary Data Analysis Plan

The primary hypothesis to be tested is that allopurinol is non-inferior to febuxostat. The primary outcome is the difference (D) in proportion of patients with one or more gout flares during Phase 3. The proposed test is a one-sided non-inferiority test of the null hypothesis that $U > B$, which the upper limit on the 95% confidence interval on the difference between two proportions exceeds 8%. We posit a true difference in proportions of 0%.

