The primary analysis for these longitudinal data will be the mixed effects model with a variance-covariance structure that assumes auto correlated AR(1) sUA measurements over time. We will use PROC MIXED in SAS. At each clinical visit a binary factor will indicate if the titration protocol is or is not maintained. Besides baseline factors such as age, sex, and duration of disease, the model will incorporate time-dependent factors including side effects. Missing data methods will address potential censoring of events among patients who fail to attend clinic visits. We will run this same analysis using the biological threshold of sUA <6.8 mg/dl after 48 weeks.

- 3) To determine if gout flares in phase 3 in participants who achieve a sUA < 6.0 mg/dl by 48 weeks differ compared to those who do not, regardless of treatment assignment.

This binary outcome for this logistic regression analysis will be the 48-week status of sUA; namely, sUA < 6 mg/dl vs sUA ≥ 6 mg/dl. The analysis will model the gout flares in phase 1 and phase 2 as time-dependent covariates as in the second secondary analysis above. Models with additional factors are described in objective 8.

- 4) To determine whether health-related quality of life measures differ between participants randomized to allopurinol compared to febuxostat and differ by achievement of sUA < 6.0 mg/dL, regardless of treatment assignment.

EQ-5D-3L & VR-12 instruments will be administered at baseline, 24 and 48 weeks. At each time we will compare the mean scores by treatment groups, using both an unadjusted t-test and linear regression with adjustment for baseline covariates. Also, with outcome change from baseline to 24 weeks and change from baseline to 48 weeks, we will compare mean changes with and without covariates using linear regression. Finally, we will carry out a repeated measures analysis using all three time points. Missing data methods will address potential censoring of events among patients who fail to complete the instrument at a particular time. Analogous analyses will be carried out controlling for sUA levels.

- 5) To determine whether change in tophi area differ by location between participants randomized to allopurinol compared to febuxostat and differ by achievement of sUA < 6.0 mg/dL, regardless of treatment assignment.

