#### **3.5.2. Secondary outcomes**

The secondary outcomes will include:

- 1) The efficacy and tolerability in patients with CKD 3.
  - i. To determine whether the efficacy of allopurinol and febuxostat differ among those with Stage 3 CKD, a planned secondary endpoint will be the occurrence of gout flares during Phase 3 in this patient subset.

- ii. Tolerability of the two treatments will also be compared in this patient subset and will include comparisons of adverse events, serious adverse events, and related study withdrawal.
- 2) The proportion of patients achieving a sUA < 6.0 mg/dl during Phase 2 (mean level assessed at weeks 36, 42, and 48) across treatment groups.
  - 3) The proportion of having at least one gout flares in Phase 3 differ in those who reach a target sUA of < 6.0 mg/dl compared with those who do not by 48 weeks.
  - 4) The impact of study treatments and sUA levels on health-related quality of life.

Both the five-item EurQol (EQ-5D-3L) and Veterans RAND 12 (VR-12) will be collected from all participants at baseline, 24, 48 and 72 weeks.

- 5) The changes in tophi area by location among those with tophaceous gout across treatment groups and sUA levels.

We anticipate that ~20% of study participants will have tophi at enrollment. The sentinel tophus will be defined as the most prominent and/or most readily measured tophus found at the time of the baseline evaluation on the hands, elbows, feet, or ears (i.e., the most common sites for tophi). Change in tophi area will be examined at week 24, week 48, and week 72 as a secondary outcome among this informative subset of patients with tophaceous gout.

- 6) The impact of treatment on the flare rate over time.

To determine whether the total number of gout flares differs between the two treatment groups the total flare numbers occurring during observation (week 0 to 72) will be compared.

Recognizing that the duration of a gout flare typically extends from several days to 2-3 weeks, and that it may sometimes be difficult for patients to distinguish between two or more back-to-back flares and one persistent but fluctuating flare, a maximum of one gout flare will be counted for each one-month observation period. Thus, as an example, during Phase 3 (24 weeks) patients could experience a number of gout flares ranging from 0 to 6 flares.

- 7) The tolerability/toxicity of the two ULTs.

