## 5.5. Secondary Analysis

All secondary analyses are descriptive exploratory analyses and will be done with and without covariate adjustment (age, sex, disease severity, comorbidities, etc.). In some secondary analyses, we will impute values to explicitly explore the effect of missing data.

We describe the proposed analysis for each of the eight secondary objectives:

- 1) To compare the efficacy and tolerability of allopurinol and febuxostat in hyperuricemic participants with gout and stage 3 chronic kidney disease (CKD 3) in reducing gout flares.
  - a. We will carry out the analogues non-inferiority analysis proposed for the primary objective but restricted to participants with stage 3 CKD, using only gout flares observed during Phase 3. Using the full cohort, we will compare gout flare rates of participants with stage 3 CKD to participants with an eGFR  $\geq 60$  mL/min/1.73m^2 with a logistic regression model.
  - b. Tolerability of the two treatments will also be compared in this patient subset and will include comparisons of proportions of adverse events, serious adverse events, and related study withdrawal during the whole study using logistic regression.
  
- 2) To explore the efficacy of the two ULT dosing regimens in achieving the goal of sUA < 6.0 mg/dl evaluated at the end of phase 2. Besides treatment, the primary predictors include the series of sUA measures and dose titrations prior to 48 weeks. This longitudinal analysis will model deviations from the titration protocol.
  - a. The analysis for these longitudinal data will be the mixed effects model with a variance-covariance structure that assumes auto correlated AR(1) sUA measurements over time. We will use PROC MIXED in SAS. At each clinical visit a binary factor will indicate if the titration protocol is or is not maintained. Besides baseline factors such as age, sex, and duration of disease, the model will incorporate time-dependent factors including side effects. Missing data methods will address potential censoring of events among patients who fail to attend clinic visits.
  - b. We will run the same analysis using the biological threshold of sUA < 6.8 mg/dl at the end of phase 2.

- 3) To determine if there are gout flares in phase 3 in participants who achieve a sUA < 6.0 mg/dl by 48 weeks differ compared to those who do not, regardless of treatment assignment.

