**Table C1. Study Primary Outcome Events**

Outcome Event Type	Sample (N= )	Element Code
Primary Outcome		
# Subjects with more than one gout flare Phase 3	N(%)	Gout flare Questionnaire and diary
Secondary outcome 1		
# Subjects with CKD3 in Phase 3	N(%)	Clinical Biochem Lab
# Subjects with more than one gout flare in Phase 3	N(%)	Gout flare Questionnaire and diary
Secondary outcome 2 and 3		
# Subjects with mean sUA < 6.0 at the end of Phase 2	N(%)	Clinical Biochem Lab
# Subjects with mean sUA < 6.8 at the end of Phase 2	N(%)	Clinical Biochem Lab
Secondary outcome 4		
EQ-5D-3L		
Mean ± SD	Mean ± SD	EQ5D-3L
Range	(range)	EQ5D-3L
VR-12		
Mean ± SD	Mean ± SD	VR-12
Range	(range)	VR-12

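### Secondary objective 3: the sUA achiever group compared on Phase 3 flares is defined inconsistently, and one of the candidate rules, the single week-48 value, is noisier than the three-visit mean the plan already schedules

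*SAP*

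**What the plan says.** The wording differs from place to place.

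- **SAP 5.5, objective 3** concerns Phase 3 flares in "participants who achieve a sUA < 6.0 mg/dl by 48 weeks differ compared to those who do not, regardless of treatment assignment". Phase 3 flare (yes/no) is the outcome of the logistic regression, so the sUA group is the exposure. No draw is named.
- **SAP 3.5.2, item 3** compares flare proportions that "differ in those who reach a target sUA of < 6.0 mg/dl compared with those who do not by 48 weeks". SAP section 2 and protocol section V use the same by-week-48 form.
- **Protocol VII, Secondary End Points, item 3** uses that form in its title, but its text compares "those who did and did not achieve a sUA of < 6.0 mg/dl at the end of Phase 2".
- **Protocol VIII, Secondary Data Analysis, objective 3** says the binary variable "will be the 48-week status of sUA; namely, sUA < 6 mg/dl vs sUA ≥ 6 mg/dl". It makes this the model outcome, the reverse of the SAP.
- **Protocol VIII, Estimated Incidence of the Primary Endpoint**, having referred to the visits at weeks 36, 42 and 48, states: "For secondary analysis, we define the binary outcome, mean sUA < 6.0 mg/dl as a treatment success".
- **SAP Tables C1 and C2**, in a block labelled for secondary outcomes 2 and 3 together, count "Subjects with mean sUA < 6.0 at the end of Phase 2".

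**The concern.** The protocol presents the link between reaching the urate target and having fewer flares as poorly documented, and as a question this design can answer. The answer depends on who is called an achiever. Different rules put different people in the groups, and an analyst could defend any of them after seeing the data.

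Two of the readings have specific weaknesses.

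- **Single week-48 value.** It carries the full visit-to-visit noise at a hard 6.0 mg/dl cut-off. Its visit window also allows it to be drawn late.
- **Ever reached target.** It counts as achievers those who reached target and then lost it. Protocol section X foresees such participants: it requires up-titration before week 36 for people off goal who had been at goal. Chances to qualify are also unequal, because the draws at weeks 9, 15 and 21 are taken only when the previous value was off target (Table 5 footnote).

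Objectives 4 and 5 also refer to achieving sUA below 6.0 mg/dl, and give no time point at all.

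**Working it through.** The plan states no power or error figure for this objective, so there is none to reproduce.

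**1. Count the rules.** Phase 2 is weeks 25-48, so its end and week-48 status are one time point. The by-week-48 form can mean ever reached or status at week 48. That leaves three rules: ever, the single week-48 value, and the mean of weeks 36, 42 and 48.

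**2. Inputs.**
- Share with a three-visit mean below 6.0: 77.5%, the middle of the protocol's expected 75-80%.
- Between-person SD of steady-state sUA: 1.0 mg/dl (assumed).
- Visit SD: 0.5 mg/dl (assumed). Protocol VII gives assay imprecision of 4-5%, which is 0.24-0.30 at 6.0. It adds that most literature finds no significant diurnal variation, while some reports suggest up to about 0.5. Treating both as SDs gives √(0.30² + 0.50²) = 0.58.
- Monthly flare risk: 3% if true sUA is below 6.0, otherwise 7% (illustrative). Six-month risks are 1 − 0.97⁶ = 16.7% and 1 − 0.93⁶ = 35.3%, a true difference of 18.6 points. The overall risk is 0.775 × 16.7 + 0.225 × 35.3 = 20.9%, close to the protocol's 20% planning rate.

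**3. Model.** True sUA is normal and each draw adds independent noise. The mean is 6 − 0.755 × √(1 + 0.25/3) = 5.21 mg/dl. Truth is true sUA below 6.0. The observed risk difference is 18.6 × (PPV + NPV − 1), where PPV is the share of labelled achievers truly below target and NPV is the share of labelled non-achievers truly above it.

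| Rule | Labelled achievers | Misclassified | PPV + NPV − 1 | Risk difference (points) |
|---|---|---|---|---|
| Mean of 36/42/48 | 77.5% | 6.7% | 0.963 + 0.831 − 1 = 0.794 | 14.8 |
| Week-48 value | 75.9% | 11.3% | 0.942 + 0.714 − 1 = 0.656 | 12.2 |
| Ever, weeks 36-48 | 87.1% | 10.1% | 0.892 + 0.947 − 1 = 0.839 | 15.6 |

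Against the mean rule, the week-48 value places 9.2% differently, or 0.092 × 900 ≈ 83 people at the protocol's 900 retained. The ever rule moves 9.6%, all into the achiever group, so non-achievers fall from about 202 to about 116.

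**4. Sensitivity.** With between-person SD 0.8-1.2, visit SD 0.25-0.60 and 75-80% achievers, misclassification is 2.7-10.2% for the mean, 4.6-16.7% for week 48, and 5.4-14.9% for any of the four Phase 2 draws. With the protocol's cited monthly rates of 6% and 14% held for six months, the true gap is 28.5 points. The observed gap is 19.5-26.1 (mean), 14.3-24.4 (week 48) and 22.7-26.6 (any value).

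**5. Timing.** Protocol Table 5 allows ±4 weeks at week 48, and Phase 3 is weeks 49-72. A draw at week 52 is within the window and could fall inside the outcome period. SAP Table A5 lists only ±2 weeks for Phases 2 and 3, which still reaches week 50.

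**The case against.** **The plan already points to the mean.** The protocol's general definition for secondary analysis and SAP Tables C1 and C2 both use it, so this could be called a missing cross-reference. That stands in part: the rule proposed below is largely the plan's own. It does not settle the matter, because the protocol's analysis text written specifically for objective 3 names week-48 status, and the SAP analysis text names nothing.

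**The stakes are limited.** SAP 5.5 calls all secondary analyses descriptive and exploratory, and the primary test does not use this grouping. That stands in full.

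A reader might also draw stronger conclusions that the documents do not support:

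- *Four competing definitions.* Two of the four wordings share a time point, and the ever reading is only one way to read the by-week-48 form.
- *The mean is free of misclassification.* Every rule misclassifies; the mean does so less.
- *The ever rule dilutes the flare contrast.* In the noise-only model it gives 15.6 points against 14.8 for the mean. Its weaknesses are the ones under the concern: lost control counted as success, and a much smaller comparison group. The model leaves out real loss of control.
- *The gout classification table's preference for urate measured away from an episode discredits a late draw.* That table is for diagnosis at entry, ideally off urate-lowering treatment, not for monitoring on treatment.
- *Noise well above 0.58 mg/dl.* Nothing in the documents supports it.

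**Conclusion.** The inconsistency is real and sits in the text: three usable rules, with no choice made in SAP 5.5(3). The protocol's week-48 rule is the noisiest of the three for the flare contrast. In the central illustration it loses 18.6 − 12.2 = 6.4 points of the true difference, against 18.6 − 14.8 = 3.8 for the mean. The ranking of week 48 below the mean holds across the assumed ranges. The sizes rest on assumed SDs, independent visit errors, stable sUA from week 36, and a flare risk that depends only on being above or below 6.0 mg/dl. The documents do not say whether a participant's Phase 3 is counted from calendar week 49 or from the actual week-48 visit, so a draw inside the outcome period is possible rather than certain.

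This is a worthwhile, low-cost clarification of an exploratory objective. It does not bear on the non-inferiority conclusion.

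**What to change.** - In SAP 3.5.2(3), SAP 5.5(3) and protocol objective 3, define an achiever as a participant whose mean of the available sUA values at weeks 36, 42 and 48 is below 6.0 mg/dl.
- Keep the on-schedule week-48 draw. Exclude any week-48 draw taken after that participant's Phase 3 flare observation has started. Section X of the protocol calls 48 weeks the start of Phase 3, so a bare before-Phase-3 cut-off could discard on-schedule draws.
- Report week-48 status as a sensitivity analysis.
- For objectives 4 and 5, use this flag only for outcomes at week 48 and later. Applied to week-24 outcomes, it would group people by sUA measured afterwards.
- Align the protocol's objective 3 model with the SAP's, with Phase 3 flare as the outcome and the sUA group as the exposure.

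**Cost:** wording only, since all three draws are already scheduled. Participants with no usable draw from weeks 36-48 will be unclassified, and some means will rest on one or two values. Both counts should be reported.

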The binary outcome for this logistic regression analysis will be the presence of gout flares in phase 3. The analysis will use gout flares in phase 1 and phase 2 as baseline covariates.

- 4) To determine whether health-related quality of life measures differ between participants randomized to allopurinol compared to febuxostat and differ by achievement of sUA < 6.0 mg/dL, regardless of treatment assignment.

- a. EQ-5D-3L & VR-12 instruments will be administered at baseline, 24, 48, and 72 weeks. At each time we will compare the mean scores by treatment groups, using both an unadjusted t-test and linear regression with adjustment for baseline covariates.

- b. With outcome change from baseline to later weeks, we will compare mean changes by treatment group with and without covariates using linear regression.

- c. We will carry out a repeated measures analysis using all time points. Missing data methods will address potential censoring of events among patients who fail to complete the instrument at a particular time.

- d. Analogous analyses will be carried out controlling for sUA levels.

- 5) To determine whether change in tophi area differ by location between participants randomized to allopurinol compared to febuxostat and differ by achievement of sUA < 6.0 mg/dL, regardless of treatment assignment.

- a. Tophi area will be assessed at baseline, 24, 48, and 72 weeks. At each time point we will compare the mean areas by location by treatment groups, using an unadjusted t-test and linear regression with adjustment for baseline covariates.

- b. With area change from baseline to later weeks, we will compare mean changes by location with and without covariates using linear regression.

- c. We will carry out a repeated measures analysis using all time points. Missing data methods will address potential censoring of events among patients who fail to complete the instrument at a particular time.

- d. Analogous analyses will be carried out controlling for sUA levels.

- 6) To determine whether the number of gout flares during all three phases differ between participants randomized to allopurinol compared to febuxostat and then extend this analysis to the entire 72-week period.

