  - a. We will model the number of gout flares, which can have substantial variation, as Poisson random variables. We will use Poisson regression to compare treatments using a longitudinal repeated measure (PROC GLIMMIX and GENMOD in SAS). Missing data methods will address potential censoring of events among patients who appear to fail to report flares.
  - b. Flare counts will be analyzed separately during Phases 1, 2, and 3 because dose titration during Phase 1 tends to increase the counts, and this effect may still persist in Phase 2, particularly for those still undergoing dose titration; participants are expected to be in steady-state by Phase 3.
  - c. Phase 2 analysis will consider prophylactic treatment after a gout flare and severe side effects of treatment as predictors of subsequent counts.
  - d. During Phase 3 the same set of factors as well as Phase 2 counts will be used to predict gout flare counts. These time-dependent associations will require a mixed effects model using an auto correlated AR(1) variance-covariance to model the series of events.
  - e. For these analyses we may treat the counts as continuous measures in order to introduce more subtle variance-covariance structure and a variety of random effects.
- 7) To determine the patterns of tolerability/toxicity for each treatment during Phase 3 and then overall from weeks 1-72.
  - a. Toxicity events include rises in sUA levels, adverse changes in serum creatinine, CBC, liver function tests (LFTs), blood pressure, and the incidence of skin rashes. The incidence of cardiovascular events of interest will also be included in this analysis.
  - b. Within each Phase we will determine if the incidence of such events differs between treatments. In the Phase 3 analysis baseline covariates will include the summary of toxicity events during Phases 1 and 2 as well as the week 48 sUA level. As in the sixth secondary analysis the same statistical methods for Poisson counts will be used.
  - c. At each clinic visit we will assess the count of each type of major side effect episodes between visits. The analyses will compare treatments using a longitudinal repeated measures analysis with Poisson count, negative binomial counts, and binary outcomes

(PROC GLIMMAX and GENMOD in SAS). Missing data methods will address potential censoring of events among patients who fail to attend clinic visits.

- 8) To describe the effects of baseline covariates and time-dependent covariates on the primary results.

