  - a. We will carry out logistic regression analyses adjusting for covariates and use GEE model.
  - b. Baseline data include demographic characteristics (e.g. age, sex), disease history including CKD level, presence of tophi at baseline, height, weight, laboratory values, medications, other comorbidities, and quality-of-life measures.
  - c. Time-dependent variables include data obtained after baseline include sUA measures, titration levels, and side effects.
  - d. All data obtained before Phase 3 may be used as baseline factors for Phase 3 analyses.

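### The Phase 3 models for objectives 6 and 7 adjust for post-randomisation variables, and the SAP does not say that the unadjusted comparison answers the objective

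*SAP*

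**What the plan says.** Objective 6 in SAP 5.5 is a comparison of randomised arms: "To determine whether the number of gout flares during all three phases differ between participants randomized to allopurinol compared to febuxostat". Items 6a and 6b plan that comparison and name no covariates: "We will use Poisson regression to compare treatments using a longitudinal repeated measure", and "Flare counts will be analyzed separately during Phases 1, 2, and 3".

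Items 6c and 6d then say what enters the later models. For Phase 2: "Phase 2 analysis will consider prophylactic treatment after a gout flare and severe side effects of treatment as predictors of subsequent counts". For Phase 3: "During Phase 3 the same set of factors as well as Phase 2 counts will be used to predict gout flare counts". Item 6d adds that a mixed model with AR(1) covariance is needed. Protocol VIII, Secondary Data Analysis, objective 6 contains the same Phase 3 sentence.

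Item 7b first asks whether event incidence differs between treatments in each phase. It then says of the Phase 3 analysis that "baseline covariates will include the summary of toxicity events during Phases 1 and 2 as well as the week 48 sUA level". Protocol VIII, objective 7 matches.

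Two general statements bear on this. SAP 5.5 opens with: "All secondary analyses are descriptive exploratory analyses and will be done with and without covariate adjustment (age, sex, disease severity, comorbidities, etc" (the list is left open). Item 8d says: "All data obtained before Phase 3 may be used as baseline factors for Phase 3 analyses".

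**The concern.** Phase 2 flares, prophylaxis given after a flare, severe side effects, Phase 1-2 toxicity and week-48 sUA are all measured after randomisation, and the assigned drug can change each of them. Week-48 sUA is the quantity that both drugs act on. A model holding them fixed compares arms among participants with the same on-treatment history. That is a different question from whether Phase 3 flares or toxicity differ by randomised arm.

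Two things can go wrong:

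- **Spurious difference.** Suppose one arm has more Phase 2 flares for reasons that do not persist. At any given Phase 2 count its participants are then on average less flare-prone, and its adjusted Phase 3 rate looks too low.
- **Attenuation.** If a treatment difference is present in both phases, the Phase 2 count absorbs part of it.

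The wording makes misreading more likely. Items 7b and 8d call these variables baseline, and SAP 5.3 dates baseline for the primary analysis to the start of Phase 3. What is at stake is how the flare-burden and toxicity results that accompany the primary result are read.

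**Working it through.** **1. The plan's own figure.** No power or effect size is stated for objective 6 or 7. The design figure is for the primary test (protocol VIII, Sample Size): power of 96%, 91% and 87% at flare rates of 15%, 20% and 25%, with 450 per arm. Power = Φ(0.08/√(2p(1−p)/450) − 1.645) gives 95.7%, 91.2% and 87.0%. The figure reproduces. It concerns the unadjusted primary comparison, which this point does not touch.

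**2. Inputs for the check.**
- From the documents: a Phase 3 flare proportion of 20%; 450 per arm; at most one flare counted per month, so 0 to 6 per phase.
- Assumed: Phase 2 proportions; any Phase 3 difference; a two-sided 5% level; a patient-level gamma frailty (mean 1, variance k = 1, 2 or 3) shared by Phases 2 and 3.

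**3. Why the coefficient moves.** Ignoring the monthly cap, a proportion p with at least one flare corresponds to a mean m = ((1−p)^(−k) − 1)/k. For a participant with y Phase 2 flares, the expected Phase 3 count is m3(1+ky)/(1+k·m2). At the same y, the allopurinol/febuxostat ratio is therefore

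(m3A/m3F) × (1+k·m2F)/(1+k·m2A) = (m3A/m3F) × ((1−p2A)/(1−p2F))^k.

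The second factor equals 1 only if the arms have the same Phase 2 rate or k = 0.

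- Phase 3 equal, Phase 2 40% v 30%: (0.60/0.70)^k = 0.86, 0.73, 0.63 for k = 1, 2, 3. The true ratio is 1.
- Phase 3 28% v 20%, Phase 2 45% v 35%: the true ratios 1.56, 1.65, 1.76 are multiplied by (0.55/0.65)^k = 0.85, 0.72, 0.61, giving 1.32, 1.18, 1.07.

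**4. Simulation.** 450 per arm, 1000 replicates, monthly cap applied. Poisson regression with robust errors was fitted to Phase 3 counts, without and with the Phase 2 count. Entries are for k = 1 / 2 / 3; the higher Phase 2 and Phase 3 proportions are placed in the allopurinol arm for illustration only.

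| Scenario | Ratio, unadjusted | Rejection, unadjusted | Ratio, adjusted | Rejection, adjusted |
|---|---|---|---|---|
| No difference in either phase (Phase 2 35% both) | 1.00 / 1.00 / 1.00 | 5 / 6 / 6% | 1.00 / 1.00 / 1.00 | 5 / 6 / 6% |
| Phase 3 equal at 20%; Phase 2 40% v 30% | 1.00 / 1.00 / 1.00 | 5 / 4 / 6% | 0.87 / 0.76 / 0.66 | 17 / 49 / 83% |
| Phase 3 equal at 20%; Phase 2 45% v 30% | 1.00 / 1.00 / 1.00 | 7 / 5 / 5% | 0.80 / 0.65 / 0.52 | 33 / 83 / 99% |
| Persistent: Phase 2 45% v 35%, Phase 3 28% v 20% | 1.52 / 1.58 / 1.64 | 87 / 89 / 95% | 1.31 / 1.18 / 1.08 | 53 / 27 / 9% |

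The adjusted ratios agree closely with step 3. Part of the rise with k comes from fixing proportions: 40% v 30% is a mean ratio of 0.667/0.429 = 1.56 at k = 1 but 1.210/0.638 = 1.90 at k = 3.

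**5. Second set, fixing the Phase 2 rate ratio.** 425 per arm, 600 replicates. The Phase 3 mean is 6 × 0.05 = 0.30, from the 5% monthly rate in protocol VIII. Frailty variance is 1.0, or 2.53, which solves (1+0.3k)^(−1/k) = 0.80. The assumed Phase 2 mean is 0.3 or 0.6.
- Phase 3 equal, Phase 2 ratio 1.5: rejection 4-6% unadjusted and 12-40% adjusted, with adjusted ratios of 0.79-0.90.
- Phase 3 equal, Phase 2 ratio 1.25: 7-16% adjusted.
- Ratio 1.5 in both phases: power 69-85% unadjusted and 16-62% adjusted.

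**The case against.** The strongest reply is that an unconditional comparison is already planned. The opening rule of SAP 5.5 requires every secondary analysis both with and without covariate adjustment, and its list of covariates is open. Items 6a and 6b give a by-phase arm comparison with no covariates named. Items 6c and 6d speak of prediction and can be read as a prognostic model. This largely stands. A reader might infer that the SAP forces conditioning and never tests Phase 3 counts by arm; the text does not support that.

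It does not close the gap. The examples in the opening rule are age, sex, disease severity and comorbidities. Objectives 4 and 5 restate their unadjusted analyses explicitly, whereas 6d and 7b do not. In 7b the covariates follow directly on the treatment question. Nothing says which estimate answers the objective, and the two can disagree.

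Other stronger readings also fail:

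- **That the arms will differ in Phase 2 by design, with bias favouring allopurinol.** Protocol X (Dosing) says the schedule was built for a similar speed of sUA reduction in both arms. SAP Table 1 lists maximum doses, and both maxima are available by week 21.
- **That objective 6 is the only flare-burden analysis and objective 7 the only modelled safety comparison.** SAP 3.5.1 also examines monthly intervals with treated flares in Phase 3. Objective 1b models adverse events in CKD 3, item 7c compares treatments without naming the 7b covariates, and SAP 3.7 reports event rates by arm.
- **That the simulated percentages are properties of the planned analysis.** They come from a Poisson regression with one added covariate, for flares only. The AR(1) mixed model and the toxicity model were not simulated.

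**Conclusion.** The point holds in limited form. The Phase 3 arm coefficients from the models described in 6d and 7b do not estimate the effect of randomised treatment on Phase 3 flares or toxicity, and the SAP does not name the unadjusted run as the answer.

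For flares, distortion needs two conditions: a Phase 2 difference between arms and within-patient correlation. Without a Phase 2 difference the error rate stays near 5%. With one, the illustrations range from slight (7% rejection under equal Phase 3 rates) to severe (99%), and attenuation from moderate to nearly complete. Which applies cannot be said, because the documents give neither Phase 2 flare rates nor a frailty variance. For 7b the reasoning is the same in kind but has not been quantified.

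A reader might infer that the trial's main conclusion is at risk. It is not: the primary test compares Phase 3 flares without covariates (protocol VIII; SAP 5.4), and objectives 6 and 7 are exploratory with no decision rule attached. Severity is minor.

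**What to change.** In SAP 5.5 (6c-6d and 7b), and in protocol VIII objectives 6 and 7:

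1. State that the Phase 2 and Phase 3 arm comparisons contain treatment and variables fixed at randomisation only, for example CKD stage 3, sUA ≥ 9.0 mg/dl, tophi, the treatment-history factor balanced at randomisation, age and sex. Report a rate ratio with its 95% CI, and say that this estimate answers the objective.
2. Move Phase 2 counts, prophylaxis after a flare, severe side effects, Phase 1-2 toxicity and week-48 sUA to a separate prognostic model. State that its arm coefficient is not interpreted as a treatment effect.

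The cost is a few sentences and no new data. The downside is losing the variance that Phase 2 counts would explain; covariates fixed at randomisation may recover part of it.
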